11.6 Handling Missing Data

Only subjects with non-missing data for safety will be used.

CP008 Revision: A Date: 13Sep2022	CONFIDENTIAL	Page 24 of 41

11.7 Interim Analysis

Interim analysis will not be conducted for this study.

12 DATA MANAGEMENT

12.1 Data Collection

Data will be collected on paper case report forms (CRF) supplied by the Sponsor. A CRF will be completed for every subject who signs a written Informed Consent Form and is enrolled in the study. The Site Principal Investigator is responsible for the accuracy and completeness of all study documentation.

Corrections to the CRF must be made by drawing a single line through the incorrect data, entering the correct data beside the incorrect entry, then initialing and dating the correction. Incorrect data must not be obscured. The use of pencil, erasable ink, or correction fluid on CRFs is prohibited. All fields must be completed, e.g., if the item was not done, mark "N/D". If the item is not applicable to an individual case, mark the field "N/A".

CRFs will be printed on 3-part No Carbon Required paper (or equivalent) so that both the site and monitor/Sponsor will have copies of the CRFs. One of the three copies may be sent to the Sponsor for remote monitoring. Any other subject information sent to the Sponsor must be redacted of personal identification information.

A unique study number will be assigned to each subject. All information recorded on the CRF about the subject will be recorded with the study number on it. The main database will contain only the study number to identify the subject. The code with subject name and study number will be maintained in a secured designated location at the site and will be inspected by study monitors and auditors. Any computerized data will be password protected.

Levita Magnetics or its designee will be responsible for database design and management for this study.

12.2 Data Processing

Prior to data entry, monitoring, as detailed below, may be completed. In association with data entry, the data will be reviewed for further inconsistencies or incongruities. All data will be collected on source documents and source document verification (SDV) will be conducted to ensure data collected are reliable and allow reconstruction and evaluation of the study. In the SDV process, information reported by the Investigator is compared with the original records to ensure that it is complete, accurate, and valid.

CP008 Revision: A Date: 13Sep2022	CONFIDENTIAL	Page 25 of 41

The Monitor shall generate queries for data errors and discrepancies discovered in their review of source documents. When queries are necessary, the Monitor will a data clarification form. Upon notification, the Investigator or designee will respond with a reason for the discrepancy and document that data is correct as documented or will provide a corrected resolution to the data field. The Monitor shall review the resolution and close the query, if appropriate. If additional information is required, the Monitor will continue the process until all data requirements are satisfied.

12.3 Final Clinical Study Report

A final report will be completed, even if the study is prematurely terminated.

12.4 Publication Policy

Information concerning the study device, patent applications, processes, unpublished scientific data, the Protocol and other pertinent information is confidential and remains the property of the Sponsor.

The clinical investigation will be registered in a publicly accessible database. At the conclusion of the trial, the results may be prepared and used in support of a regulatory submission and provided at major meeting(s). The publication of results from any center experience within the trial is not allowed unless there is written consent from the Sponsor.

A publication strategy plan will be developed as a collaboration between the Principal Investigators and the Sponsor, Levita Magnetics.

13 MONITORING AND QUALITY CONTROL PROCEDURES

13.1 Control of Systemic Error/ Bias

Clinical monitors may verify subject data and ensure compliance with Good Clinical Practices (GCPs), clinical protocol and other study requirements.

13.2 Monitoring and Auditing

Monitoring visits to the clinical sites may be made periodically during the study, to ensure that it is conducted in accordance with the protocol and the following guidelines and standards: ISO 14155, The Code of Federal Regulations 21 CFR Part 812 and country specific regulations. Levita Magnetics intends to monitor the investigational site at an interval consistent with the screening rate.

Prior to the enrollment of any subject in this study, site study personnel will be trained to the protocol and the device including the IFU. Additionally, the procedure for obtaining informed consent and the procedure for reporting adverse events will be reviewed.

The Monitor will ensure through personal contact with the Investigator and site personnel that the members of the clinical staff clearly understand and accept the obligations incurred in this investigation, and that these obligations are being fulfilled throughout the study. Specifically, the Monitor will interact with the site via telephone contact and potentially periodic on-site visits to ensure that:

- Qualified subjects are appropriately consented
- Regulatory and study documents are complete and current
- The protocol is appropriately followed
- Protocol amendments have been approved by the EC, the hospital director (as applicable), and the Sponsor has received the approval in writing
- Accurate, complete, and current records are maintained for all subjects
- Source data verification may be undertaken to ensure the information recorded and submitted to the Sponsor is representative of the subject record and other supporting documentation
- Inconsistent and incomplete data are addressed and resolved
- Accurate, complete, and timely adverse event reports are being made to the Sponsor
- Investigational devices are properly stored, and accounted for

The Investigator or designee must, upon request, provide to the Monitor or regulatory authority the necessary study records for a thorough review of the study's progress. These records include, but are not limited to, case report forms, original documents, records such as hospital and clinic charts, consent forms, laboratory records, and any other study related documents.

The Monitor will provide a written report to the Sponsor after each on-site visit. The report will identify the personnel participating in the visit, the activities performed, any protocol deviations, and any action items/corrective actions identified.

If compliance problems or protocol deviations are noted, the Sponsor will recommend corrective action. If the response from the Investigator is not adequate, the Sponsor will terminate the site's participation in the study and notify EC and the regulatory authorities (if applicable).

The study may also be subject to a quality assurance audit by the Sponsor or its designees, as well as inspection by appropriate regulatory authorities.

It is important that the Investigator and relevant study personnel are available during the monitoring visits and possible audits and that sufficient time is devoted to the process.

13.3 Device Accountability

The device is investigational and not approved for commercial use. Access to investigational devices shall be controlled and used only in the clinical investigation and according to the protocol.

The Sponsor shall keep records to document the physical location of all investigational devices from shipment (or hand-carried) to the sites until return or disposal.

The site Principal Investigator or an authorized designee shall keep records documenting the receipt, use, return, and disposal of the investigational device, which shall include:

- The date of receipt
- Identification of each investigational device (lot number)
- The date of use
- Subject study identification number
- Date of return of unused or malfunctioning investigational devices, if applicable
- Date of disposal, if applicable

The Investigator must explain in writing the reasons for any discrepancy noted in device accountability.

14 ADVERSE EVENTS

14.1 Definitions

14.1.1 Adverse Event (AE)

AEs are any untoward medical occurrence, unintended disease or injury, or untoward clinical signs (including abnormal laboratory findings) in which subjects, users, or other persons, whether or not related to the investigational medical device. This definition includes events related to the procedures involved. For users or other persons, this definition is restricted to events related to investigational medical devices.

All adverse events, regardless of relationship to the device, must be recorded on the case report forms provided. Adverse events that occur during this study should be treated by established standards of care.

Adverse events shall be assessed by the Investigator as to its relationship and level of relatedness to the investigational device, assessment, and/or procedure, and documented at the time of the procedure and at all study follow-up visits.

Each Investigator shall provide source documentation as requested by the Sponsor to facilitate reporting and adjudication of these events.

14.1.2 Serious Adverse Event (SAE)

An adverse event is considered "serious" if, in the view of either the Investigator or Sponsor, it results in any of the following outcomes:

- Death
- Life-threatening
- Hospitalization (initial or prolonged)
- Disability or permanent change
- Congenital Anomaly/Birth Defect
- Required Intervention to Prevent Permanent Impairment or Damage
- Other Serious (Important Medical Events)

Planned hospitalization for a pre-existing condition, without serious deterioration in health, is not considered a serious adverse event.

14.1.3 Serious Adverse Device Effect (SADE)

A serious adverse device effect is defined as an adverse event related to the use of an investigational medical device that has resulted in any of the consequences characteristic of a serious adverse event.

14.1.4 Unanticipated Serious Adverse Device Effect (USADE)

An USADE is a serious adverse device effect which by its nature, incidence, severity or outcome has not been identified in the current version of the investigational plan.

14.2 Adverse Event Reporting

Any adverse event that occurs during the course of the study must be reported using the Adverse Event (AE) Form in the CRFs and the Investigator must sign each report. The Investigator must determine whether the adverse event is serious or unanticipated, its severity, and the relationship of each adverse event to the investigational device or procedure. In addition, the Investigator will identify the date of onset and duration of the AE.

Pre-existing medical conditions or symptoms occurring prior to the laparoscopic procedure involving the MSS should not be reported as adverse events, unless there is a worsening of the pre-existing medical condition.

All serious adverse events, including unanticipated serious adverse device effects, must be reported to the Sponsor within 24 hours of the site first becoming aware of the event via email ([contact]). At a minimum,

the AE CRF should be provisionally completed, scanned and sent via email. The Sponsor will contact the site for additional information, if required.

For any adverse event that is ongoing at the time of the initial report, periodic follow-up information is required until the adverse event is resolved or is not expected to change. The site should submit relevant follow-up information related to the adverse event as soon as it is available. All adverse events will be monitored until they are adequately resolved or explained. If an AE continues after the study participation ends, the Sponsor and Investigator should discuss the need and/or methods for continued surveillance of the event.

Depending upon the nature and seriousness of the adverse event, the Sponsor may request the Investigator to provide copies of the subject's medical records (such as the subject's laboratory tests and hospital records, Investigator summaries, etc.) to document the adverse event. The Sponsor is available to respond to any medical issues that arise during the conduct of this study.

The Investigator will report all adverse events, including serious and unanticipated serious adverse device effects, to the reviewing EC according to the local reporting requirements. A copy of this EC communication should be sent to the Sponsor.

The Sponsor will ensure that safety reporting for the study is conducted in compliance with all pertinent requirements and regulations.

The Sponsor's evaluation of UADEs must be reported to the FDA, all reviewing ECs, and participating Investigators within 10 working days of knowledge of the event by the Sponsor. All UADE will be reported to the FDA according to regulatory reporting requirements found in CFR 812.46.

14.3 Adverse Event Severity

The Investigator must determine the severity of the adverse event according to the following definitions:

Mild The adverse event is noticeable to the subject but does not interfere with routine activity; the symptoms are easily tolerated and transient in nature.

Moderate The adverse event interferes with routine activity but responds to symptomatic therapy or rest; the symptoms are poorly tolerated and sustained.

Severe The adverse event significantly limits the subject's ability to perform routine activities despite symptomatic therapy. The adverse event requires medical or surgical treatment or results in hospitalization.

Life-Threatening The subject is at immediate risk of death.

14.4 Event Relationship

The following lists the potential event attribution categories.

14.4.1 Device Related

An adverse event is considered device-related when the clinical event has a reasonable time sequence associated with use of the investigational device and is unlikely to be attributed to concurrent disease or other procedures or medications. It is reasonable to believe that the device directly caused or contributed to the adverse event.

The Investigator will evaluate the relationship of the adverse event to the MSS and/or DRAA according to the following definitions:

Definite The adverse event is clearly related to the investigational device: the event has a temporal relationship to the investigational device, follows a known pattern of response, or is otherwise logically related to the investigational device, and no alternative cause is present.

Probable The adverse event is likely related to the investigational device: the event has a temporal relationship to the investigational device, follows a known or suspected pattern of response, or is otherwise logically related to the investigational device, but an alternative cause may be present.

Not likely The adverse event is unlikely related to the investigational device: the event does not follow a clear temporal relationship to the investigational device or does not follow a known pattern of response or is otherwise likely to be due to the subject's clinical state or other modes of therapy.

Not related The adverse event is clearly not related to the investigational device: the event has no temporal or other relationship to the administration of the investigational device, follows no known or suspected pattern of response, and an alternative cause is present.

Unknown Unable to determine the relationship based on all available information.

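### In 14.4.1 and 14.4.2, lack of a known response pattern is enough by itself for a Not likely rating, so the causality categories overlap and a novel effect of the robotic accessory may be under-attributed

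*Combined protocol and SAP*

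**What the plan says.** Section 14.4.1 opens with a general definition of device-related. It asks whether the event "has a reasonable time sequence associated with use of the investigational device and is unlikely to be attributed to concurrent disease" (other procedures and medications are named as well), and has no test of response pattern. Five ratings follow:

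- *Definite*: a temporal relationship, then "follows a known pattern of response, or is otherwise logically related to the investigational device, and no alternative cause is present".
- *Probable*: a temporal relationship, then "follows a known or suspected pattern of response, or is otherwise logically related to the investigational device, but an alternative cause may be present", so the condition on other causes is weaker.
- *Not likely*: three conditions, covering unclear timing, lack of a known pattern, and a likelier source in the patient's condition or other treatment. They are linked as follows: "or does not follow a known pattern of response or is otherwise likely to be due".
- *Not related*: no temporal or other relationship, and the event "follows no known or suspected pattern of response, and an alternative cause is present".
- *Unknown*: the relationship cannot be determined.

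Section 14.4.2 uses the same structure for the procedure.

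The rating has consequences elsewhere. Sections 7.1 and 11.3 summarise adverse events by relatedness and split device-related events by MSS, DRAA or both. Section 11.4 reports device-related events and device-related serious events. A SADE (14.1.3) must be related to the device, and a USADE (14.1.4) is a SADE that "by its nature, incidence, severity or outcome has not been identified in the current version of the investigational plan". On expedited reporting, 14.2 says: "The Sponsor's evaluation of UADEs must be reported to the FDA", with a limit of 10 working days.

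**The concern.** A causality scale should place an event in one category, or say which category wins when two fit. Here one limb of *Not likely* depends only on what is already known about the device. That limb weighs most on the DRAA, the component under study: the clinical experience cited in 3.1 is with the MSS, so there is little response history for the accessory to draw on.

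The trial is single-arm (8.1), so the investigator's attribution is the main means of separating device effects from those of the surgery. If a novel event is rated *Not likely*, it may drop out of the device-related tables. If it is serious, it may also not count as a SADE, and so not as a USADE or a reported UADE. Two investigators could follow the text faithfully and give the same event opposite ratings.

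**Working it through.** No figure in the plan bears on this point, so the check is logical. I set the category definitions in 14.4.1 side by side and listed every combination of the features they use.

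**Features.** T: clear temporal relationship. K: known pattern. S: suspected pattern. L: otherwise logically related. A: alternative cause present. O: otherwise likely due to clinical state or other therapy. A known pattern counts as at least a suspected one (K implies S), and a likelier other cause is an alternative cause (O implies A). Combinations: 2 (T) × 3 (K, S) × 2 (L) × 3 (A, O) = 36.

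**Rules.**
- *Not likely* = not T, or not K, or O.
- *Not related* = not T, not L, not S, and A.
- *Definite* and *Probable* can be read in two ways. In reading (a) the comma list is a chain of alternatives: *Definite* = (T or K or L) and not A; *Probable* = T or K or S or L. In reading (b) timing is required: *Definite* = T and (K or L) and not A; *Probable* = T and (K or S or L).

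**All combinations.** *Not likely* fails only when T and K hold and O does not: 2 (L) × 2 (A) = 4 combinations. It is met in 36 − 4 = 32, including every combination without a known pattern. Of those 32, *Definite* or *Probable* is also met in 29 under (a) and 11 under (b).

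**The novel event.** Fix T = yes, K = no, O = no. That leaves 2 (S) × 2 (L) × 2 (A) = 8 combinations.

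| Rating | Reading (a) | Reading (b) |
|---|---|---|
| *Not likely* met | 8 of 8 | 8 of 8 |
| *Definite* or *Probable* also met | 8 of 8 | 6 of 8 |
| *Not related* met | 0 of 8 | 0 of 8 |

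The 2 combinations that fall to *Not likely* alone under (b) have neither a suspected pattern nor a logical link to the device.

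**A mismatch in wording.** *Probable* and *Not related* refer to a known or suspected pattern; *Not likely* refers only to a known one. An event with clear timing and only a suspected pattern therefore meets *Probable* and *Not likely* together.

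**With the known-pattern limb deleted.** *Not likely* becomes not T, or O. It is met in 18 (not T) + 6 (T and O: 3 × 2) = 24 combinations, and in 0 of the 8 novel ones, since each has T and lacks O. Overlap with *Definite* or *Probable* falls from 29 to 21 under (a) (24 less the 3 with no T, S or L) and from 11 to 5 under (b) (the 6 with T and O, less the 1 with neither S nor L). Under (b), the 2 combinations with neither a suspected pattern nor a logical link then go to *Unknown*.

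The counts describe how the definitions intersect. They are not event probabilities.

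**The case against.** A reader might infer that a novel effect must be rated unrelated and can never become an unanticipated device effect. The text does not support that. *Not related* is a separate category whose conditions must all hold, including an alternative cause. *Definite* stays open through a logical link and *Probable* through that or a suspected pattern. Each rating is also headed by an overall assessment, and an investigator who believes the device caused the event would not naturally choose a rating headed as unlikely related.

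Other safeguards stand. Every SAE goes to the sponsor within 24 hours whatever its relatedness, and the investigator reports all adverse events to the ethics committee (14.2). Source documents are to support adjudication (14.1.1). The sponsor assesses device deficiencies that could have led to a SADE (14.6). One termination reason in 15.10 concerns events of unknown nature and carries no relatedness condition. A USADE can also be unanticipated by incidence, severity or outcome, where the pattern may be well known.

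These arguments limit the consequence but do not remove the overlap. The open routes to *Definite* and *Probable* are the reason one event fits opposite ratings. The safeguards are partial: 14.1.2 gives the sponsor a say on seriousness, but 14.1.1, 14.2 and 14.4.1 assign relatedness to the investigator, and no procedure for re-rating is described. Non-serious device-related events do not have the 24-hour route.

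**Conclusion.** The point holds as a contradiction within the rating scales. Lack of a known pattern alone satisfies *Not likely*, the same event can satisfy *Definite* or *Probable*, and the plan gives no order of precedence and does not say which ratings count as device-related. Novel device effects may therefore be rated inconsistently or under-attributed.

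No numerical size can be given. It would be tempting to say that one misrated event turns 1/50 into 0/50. That assumes an event rate the documents do not give, a misrating, and a summary that counts *Not likely* as unrelated, which the plan does not state. Nor is a one-way bias shown: under reading (a), timing alone can satisfy *Probable*, and *Definite* where there is no alternative cause, which pushes the other way. It would also go too far to say that every event missing from the 10.2 risk list is affected. That list says it is incomplete, and 14.4.1 does not define a known pattern by reference to it.

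The conclusion rests on reading or in its ordinary sense in *Not likely*. It holds under both readings of *Definite* and *Probable*.

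**What to change.** In 14.4.1 and 14.4.2:

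1. Delete the known-pattern limb from *Not likely*, keeping the timing limb and the other-cause limb joined by or. Joining them by and would leave an event with clear timing but a likelier other cause without a fitting rating.
2. Add a sentence that absence of a known pattern of response is not by itself a reason to rate *Not likely*.
3. State in section 11 which ratings, including *Unknown*, count as device-related in the summaries.

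Some overlap remains where an event has clear timing but another cause is likelier, and under reading (a) also where timing is unclear. One line saying which rating then prevails would settle it.

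The cost is a few sentences in the protocol and matching text on the adverse event form, with no new data and no change in sample size. The downside is that a few more events may be rated related.
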